### 6.2. *Study Endpoints*

#### 6.2.1. Primary Safety Endpoint

The primary safety endpoint will be evaluated by the safety event free rate at 12 months post-index procedure.

*Primary safety events will consist of a composite of the following procedure-related and device-related adverse events.*

*Acute primary safety endpoint events, events occurring up to 7 days post-index procedure or hospital discharge, whichever is later, include:*

- Death
- Myocardial infarction (MI)
- Persistent gastroparesis/injury to vagus nerve
- Transient ischemic attack (TIA)
- Stroke/Cerebrovascular accident (CVA)
- Thromboembolism/ Air embolism\*
- Cardiac tamponade/perforation
- Pneumothorax
- Serious vascular access complications\*\*
- Pulmonary edema/heart failure
- AV block not attributable to medication effect or vasovagal reaction

\*Thromboembolic or air embolic events collected in the study refer to any occlusion of blood vessel(s) that results in clinical symptoms

\*\* Defined as prolongation of hospitalization, requirement of surgical intervention or blood transfusion

*Chronic primary safety endpoint events, events occurring through 12 months post-index procedure, include:*

- Atrial esophageal fistula
- Pulmonary vein stenosis ( $\geq 70\%$  reduction of diameter)
- Symptomatic pericardial effusion
- Persistent Phrenic nerve injury\*\*\*

\*\*\*A non-recovered phrenic nerve injury at 12 months post-index procedure will count as a chronic primary endpoint. The study will collect information on phrenic nerve palsy observed before the end of the index procedure and, in case it occurred, will track information for potential recovery during the study visits.

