### 7.2. ***Treatment Assignment***

Any subject who signs the consent form will be considered enrolled in the study.

Any subject that signs the consent form, has the study device inserted into the body and undergoes the protocol specific treatment for the intended disease (cryoablation) will be assigned to the treatment group.

Enrollment will progress until reaching a minimum of 200 subjects and a maximum of 400 subjects. A minimum of 199 De Novo (ie. first treatment for AF in the left atrium) TREATMENT subjects with PAF is needed for the assessment of the primary endpoint statistical hypothesis testing (section 11.1).

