### 11.1.1.2. Sample Size

### 11.1.1.3. Statistical Methods

The 12 month (365-day) primary safety event-free rate will be calculated using Kaplan-Meier methodology. Subjects who withdraw from the study prior to 12 months without experiencing an event will be censored on the date of withdrawal. The 95% one-sided lower confidence limit of the observed safety event-free rate will be compared to the performance goal of 86%. If the lower confidence limit is greater than the performance goal, the null hypothesis will be rejected. The lower confidence limit will be calculated as the pointwise confidence limit using the log-log methodology.

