**23.2. Definitions**

Terms are defined in Table 23.2-1.

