**Table 23.2-1 Definitions**

Term	Definition
Activated Coagulation/Clotting Time	ACT is a test that is used to monitor the effectiveness of high dose heparin therapy.
Arterial-Venous Fistula	Abnormal communication between an artery and a vein.
Atrioesophageal Fistula	A connection between the atrium and the lumen of the esophagus.
Attempt Subject	Any subject that signs the consent form, and has any study device inserted into the body but does not receive any Cryoablation application.
AV block	A conduction disturbance that results in the partial inability of an electrical impulse generated in the atria to reach the ventricles.
Blanking Period	90-day period between ablation procedure and the initiation of the Effectiveness Evaluation Period during which up to one additional ablation procedure can be performed and subjects can be prescribed antiarrhythmic drugs as determined necessary by the investigator.
Cardiac tamponade/ perforation	The development of a significant pericardial effusion during or within 30 days of undergoing an AF ablation procedure. A significant pericardial effusion is one that results in hemodynamic compromise, requires elective or urgent pericardiocentesis, or results in a 1-cm or more pericardial effusion as documented by echocardiography.
Embolism	The sudden blocking of an artery by a clot or foreign material which has been brought to its site of lodgment by the blood current.
Enrolled Subject	A subject who has given written informed consent to participate in the study.
Hematoma	A localized collection of blood, usually clotted, in an organ, space or tissue, due to a break in the wall of a blood vessel.
Intent Subject	Any subject that signs the consent form but does not have any study devices inserted into the body. Subjects who are enrolled in the study but do not undergo ablation procedure within 90 days from consent signature date may not be reconsented and will be withdrawn from the study.

Term	Definition
In-patient Hospitalization	Hospitalizations $\geq 24$ hours in duration or $<24$ hours with medical intravenous therapy or surgical intervention

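### Read literally, the Table 23.2-1 definition of AV block omits complete block, while the primary safety endpoint lists count AV block of any degree

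*Combined protocol and SAP*

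**What the plan says.** The composite primary safety endpoint includes, among its acute events, "AV block not attributable to medication effect or vasovagal reaction". The same item appears in the synopsis, in section 6.2.1 and in section 11.1.1. None of the three lists states a degree or severity. The only carve-outs concern cause: medication effect and vasovagal reaction.

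Section 23.2 introduces the glossary with "Terms are defined in Table 23.2-1". The AV block entry there reads "A conduction disturbance that results in the partial inability of an electrical impulse generated in the atria to reach the ventricles". It is the only definition of AV block in the document. No other section mentions complete block, and none says that the endpoint lists take precedence over the glossary.

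On the analysis, section 11.1.1.3 compares the one-sided 95% lower confidence limit of the 12-month Kaplan-Meier event-free rate with a performance goal of 86%. It adds: "The lower confidence limit will be calculated as the pointwise confidence limit using the log-log methodology". Section 7.2 gives the size of the tested population: "A minimum of 199 De Novo (ie. first treatment for AF in the left atrium) TREATMENT subjects with PAF is needed".

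**The concern.** In complete AV block no atrial impulse reaches the ventricles. That is not a partial inability, so the one available definition does not describe it on its plain words. Intermittent block would meet the definition and the more severe form would not. The endpoint lists, which do not limit degree, give no sign that this ordering was intended.

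No other listed component reliably picks up the event. A procedure-related complete block that led to death or heart failure in the acute window would count through those items. One that led to neither matches nothing else in the composite.

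At stake is the classification of one component of a primary endpoint in a single-arm study. If the definition were applied as written, such a subject would be event-free unless another primary event occurred. Leaving an event out can only raise the estimated event-free rate, so any error runs in the device's favour.

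**Working it through.** **Comparison of the texts**

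| Place | What it covers | Limits stated |
|---|---|---|
| Synopsis, 6.2.1, 11.1.1 | AV block as an acute primary safety event | Cause only (medication, vasovagal); no degree |
| Table 23.2-1 | AV block as a conduction disturbance | Partial failure of conduction only; nothing on cause |

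The two agree for partial block. They diverge for complete block: the lists include it on their face, and the glossary entry does not.

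Some entries in Table 23.2-1 do set endpoint criteria. The pulmonary vein stenosis entry states a criterion expressly for the primary safety endpoint, and the myocardial infarction and stroke entries give diagnostic criteria for listed events. The table therefore cannot be set aside as pure background, although the AV block entry itself says nothing about the endpoint.

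**Scale of a misclassification**

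The plan gives no AV block rate and no figure that depends on this definition, so there is nothing of its own to reproduce. The following is for scale only.

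Inputs:
- Performance goal 86%, one-sided 95% limit, log-log method (section 11.1.1.3).
- n = 199, the minimum for hypothesis testing (section 7.2).
- No censoring before 12 months (assumption).

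Without censoring, with x events among n subjects:
- S = 1 − x/n
- Greenwood sum v = x / [n(n − x)]
- Standard error on the log-log scale = √v / |ln S|
- Lower limit = S^exp(1.645 × standard error)

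For x = 19:
- S = 180/199 = 0.9045, ln S = −0.1003
- v = 19/(199 × 180) = 0.000530, √v = 0.02303
- Standard error = 0.02303/0.1003 = 0.2295
- Lower limit = 0.9045^exp(0.3775) = 0.9045^1.459 = 0.8638, above 0.86: pass

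For x = 20:
- S = 179/199 = 0.8995, ln S = −0.1059
- v = 20/(199 × 179) = 0.000561, √v = 0.02370
- Standard error = 0.02370/0.1059 = 0.2237
- Lower limit = 0.8995^exp(0.3680) = 0.8995^1.445 = 0.8581, below 0.86: fail

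| Events of 199 | Event-free rate | Lower limit | Against 86% |
|---|---|---|---|
| 18 | 90.95% | 0.8696 | pass |
| 19 | 90.45% | 0.8638 | pass |
| 20 | 89.95% | 0.8581 | fail |
| 21 | 89.45% | 0.8524 | fail |

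Each subject is worth 1/199 = 0.5 percentage point. If complete block occurred in 0% to 1% of subjects (an assumed range), that is 0 to 2 subjects (0.01 × 199 = 1.99). One omitted event changes the conclusion only if the true count is 20. Two omitted events change it only if the true count is 20 or 21.

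**The case against.** The strongest case against is that this is one loose adjective in a glossary. The endpoint lists are the operative text, and a sponsor who wanted to exclude complete block would have written the exclusion there, next to the medication and vasovagal carve-outs. Many glossary entries are descriptive, and the AV block entry has none of the endpoint wording found in the pulmonary vein stenosis entry. Section 19.1 gives review and classification of events to a sponsor group that includes physicians with electrophysiology expertise, who would hardly score a complete block as no block. Section 17.1 makes all serious and all study-procedure-related adverse events reportable, so the event would be seen in any case.

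Most of this stands. A reader might infer that the plan excludes complete block from the primary endpoint, or that events will be classified strictly by the glossary. The documents support neither. No section binds classification to Table 23.2-1, and nothing suggests that the exclusion was chosen.

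What remains is narrower. Reporting under section 17 does not by itself make an event a primary endpoint event. The only written definition, in a table that sets criteria for other components, is at odds with the lists.

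It is also fair to say that adding complete block would still leave open whether conduction delay alone, or transient block during the procedure, counts. Those are separate ambiguities and do not remove this one.

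**Conclusion.** The point holds as a drafting error of low severity. On its plain words the Table 23.2-1 definition omits complete AV block, and the endpoint lists do not.

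The consequence is conditional. Only if the definition is applied as written would a procedure-related complete block without another primary event be missing from the rate tested against 86%. The direction of that error is certain, since it can only help the device, but its expected size is very small. It could alter the conclusion only near the boundary between 19 and 20 events.

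That boundary assumes exactly 199 subjects and no censoring. The 199 is a minimum, section 11.3.1 uses all available TREATMENT subjects for safety, and withdrawals would be censored, so the actual boundary may differ. The 0% to 1% rate is an assumption, because the documents give none.

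It would go too far to conclude that the trial's safety result is biased or that complete block would escape safety oversight.

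**What to change.** In the AV block entry of Table 23.2-1, change the wording to *partial or complete inability*. Leave the medication and vasovagal exclusions in the synopsis and in sections 6.2.1 and 11.1.1 as they are. If the sponsor did mean to leave complete block out, the endpoint lists should say so and give the reason.

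The cost is two added words in the definitions table. No new data, analysis or sample size change is needed. The change should be in place before events are classified for the primary safety analysis.

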## 19. Committees

### 19.1. *Safety Monitoring Process*

BSC Safety Trial Operations reviews all reported adverse events and device deficiencies on a regular basis and, as required, with BSC Medical Safety per the study specific safety plan. During scheduled monitoring activities, clinical research monitors will support this continuous review through their review of source documents and other data information. The BSC Medical Safety group includes physicians with expertise in Electrophysiology and with the necessary therapeutic and subject matter expertise to evaluate and classify the events into the categories outlined above.

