Myocardial infarction (in the context of AF ablation)	
The presence of any one of the following criteria:
 
 
(1) detection of ECG changes indicative of new ischemia (new STT wave changes or new LBBB) that persist for more than 1 hour;
 
(2) development of new pathological Q waves on an ECG;
 
(3) imaging evidence of new loss of viable myocardium or new regional wall motion abnormality
 

Occlusion Grade	
Score 4 = excellent (full retention of contrast medium without visible outflow)
 
Score 3 = moderate (incomplete occlusion with slight leakage of contrast medium)
 
Score 2 = poor (presence of sustained and massive leakage of contrast medium)
 
Score 1 = very poor (immediate rapid outflow from the PV).

Paroxysmal Atrial Fibrillation (PAF)	Recurrent symptomatic Atrial Fibrillation that terminates spontaneously or with intervention within seven days of onset.
Pericardial Effusion	A collection of fluid or blood in the pericardial space around the heart or in pleural space around the lungs.
Pericarditis	Inflammation of the pericardium surrounding the heart. Pericarditis should be considered a major complication following ablation if it results in an effusion that leads to hemodynamic compromise or requires pericardiocentesis, prolongs hospitalization by more than 48 hours, requires hospitalization, or persists for more than 30 days following the ablation procedure.
Pneumothorax	Collapse of the lung due to an abrupt change in the intrapleural pressure within the chest cavity.
Primary Effectiveness Failure	
A TREATMENT subject with
 
 
• Acute procedure failure
 
• More than one repeat procedure during the blanking period
 
• Documented atrial fibrillation, or new onset of atrial flutter or atrial tachycardia event (<math>\geq 30</math> seconds in duration from an event monitor or Holter, or from a 10 second 12-lead ECG) between 91 and 365 days post index procedure
 
 
Any of the following interventions for atrial fibrillation, or new onset of atrial flutter or atrial tachycardia between 91 days and 365 days post index procedure:
 
 
• Repeat procedure
 
• Electrical and/or pharmacological cardioversion for AF/AT/AFL
 
• Prescribed a higher dose of any AAD documented at baseline or a new AAD not documented at baseline
 

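### The glossary definition of pericardial effusion includes pleural fluid, so a related symptomatic pleural effusion could be counted as a chronic primary safety event

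*Combined protocol and SAP*

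**What the plan says.** Section 6.2.1 introduces the long-window part of the composite with "Chronic primary safety endpoint events, events occurring through 12 months post-index procedure, include" and lists four items, one of which is "Symptomatic pericardial effusion". The synopsis and section 11.1.1 carry the same item. The footnotes in all three places qualify embolic events, vascular access complications and phrenic nerve injury; none qualifies effusion. The composite as a whole is limited by relatedness: "Primary safety events will consist of a composite of the following procedure-related and device-related adverse events".

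For the meaning of terms, section 23.2 states "Terms are defined in Table 23.2-1". The Pericardial Effusion row of that table reads "A collection of fluid or blood in the pericardial space around the heart or in pleural space around the lungs".

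The component feeds a formal test. Section 11.1.1.3 says "The 95% one-sided lower confidence limit of the observed safety event-free rate will be compared to the performance goal of 86" percent, using a Kaplan-Meier estimate and a log-log pointwise limit.

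**The concern.** Fluid in the pleural space is a pleural effusion, which no endpoint section lists. The definition therefore reaches further than the name of the component it serves. A classifier who applies Table 23.2-1 would count a related symptomatic pleural effusion; one who goes by the ordinary meaning of pericardial would not. A component of a hypothesis-tested endpoint should not turn on that choice, and the choice should not be left until events are known.

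**Working it through.** **The text**

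| Place | How effusion is used |
|---|---|
| Sections 6.2.1 and 11.1.1, and the synopsis | Pericardial, symptomatic, through 12 months; not defined there |
| Table 23.2-1, Pericardial Effusion | Pericardial space or pleural space |
| Table 23.2-1, Cardiac tamponade/perforation | Cardiac only: "A significant pericardial effusion is one that results in hemodynamic compromise, requires elective or urgent pericardiocentesis", or at least 1 cm on echocardiography |
| Table 23.2-1, Pericarditis | Cardiac only: hemodynamic compromise or pericardiocentesis |

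The Pericardial Effusion row is the only one that brings in the pleura, and no other section narrows it.

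**Scale**

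The plan states no figure that depends on this definition, and the sample-size inputs are not in the public text, so there is nothing to reproduce. What follows shows scale only.

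Inputs: N = 199, the minimum number of De Novo paroxysmal subjects for the primary test (section 7.2); goal 86% and one-sided 95% limit, z = 1.645 (section 11.1.1.3). Assumption: no censoring, so the Kaplan-Meier rate is a simple proportion.

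With e subjects having an event:

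- S = 1 − e/N
- SE of log(−log S) = √[e / (N(N − e))] / |ln S|
- Lower limit = S^exp(z × SE)

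For e = 19: S = 180/199 = 90.45%. SE = √[19/(199 × 180)] / 0.1003 = 0.02303/0.1003 = 0.2295. Exponent = exp(1.645 × 0.2295) = 1.459. Lower limit = 86.38%, above 86%.

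For e = 20: S = 179/199 = 89.95%. SE = √[20/(199 × 179)] / 0.1059 = 0.02370/0.1059 = 0.2237. Exponent = exp(1.645 × 0.2237) = 1.445. Lower limit = 85.81%, below 86%.

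So up to 19 events pass and 20 do not. One more subject with an event costs 1/199 = 0.50 percentage points, provided that subject has no other primary event.

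The documents give no rate for related symptomatic pleural effusion. Over an assumed range of 0 to 1%, the added events are 199 × 0 = 0 up to 199 × 0.01 ≈ 2.

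The chance of passing is P(X ≤ 19) with X binomial (199, 1 − p). The true event-free rate p is not public, so the rates below are assumptions. The last column is the upper end of the assumed range; at the lower end nothing changes.

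| True rate p | No pleural events counted | 1 point lost to pleural events |
|---|---|---|
| 90% | 47.5% | 30.2% |
| 92% | 82.7% | 66.4% |
| 95% | 99.75% | 98.3% |

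**The case against.** The route to a wrong count is narrow. The component itself says pericardial. Section 17.1 asks sites to report the medical diagnosis as the event term wherever possible, so a pleural effusion would normally arrive under its own name. Section 19.1 then has sponsor physicians with the "subject matter expertise to evaluate and classify the events into the categories outlined above". This stands as a reason to expect few misclassified events. It does not remove the defect, because neither section states a narrower definition and Table 23.2-1 is the stated source of terms.

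It can also be said that deleting the clause guesses at intent, since the sponsor may have wanted to capture thoracic fluid or blood more broadly. The documents do not settle this, and the fix allows for it.

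A reader might infer that any symptomatic pleural effusion would count. It would not: the composite takes only procedure-related and device-related events. Nor do the documents say that a grade of possibly related is enough; Table 17.3-1 lists five relationship categories, and no section says which of them qualify for the endpoint.

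A reader might also take 19 events and 0.5 points as fixed. They are not protocol figures. Section 11.3.1 uses all available TREATMENT subjects for safety and enrollment may reach 400. In a larger set one event weighs less (1/400 = 0.25 points at that ceiling) and the limit is not 19. Because the endpoint counts subjects, a pleural effusion in someone who also has, say, tamponade adds nothing.

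**Conclusion.** Wrong as written, minor. The Pericardial Effusion row does not match the endpoint component that relies on it, and followed literally it would add related symptomatic pleural effusions to the chronic primary safety events. The error runs against the device: it can lower the event-free rate but cannot hide harm or yield a false success.

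The size is 0 to 2 events at an assumed frequency of 0 to 1%, that is, 0 to 1 percentage point, given N = 199, no censoring and no other primary event in the same subjects. It would affect the conclusion only if the count were already close to the 19/20 boundary. The documents do not support reading it as a material threat to the safety test, since they give neither a frequency of such events nor an expected event-free rate.

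**What to change.** Before events are classified, delete the closing clause of the Pericardial Effusion row in Table 23.2-1, the part that adds the pleural space, so that the row matches the endpoint term. If pleural collections are meant to count, keep the row purely pericardial and list pleural effusion as a separate component in the synopsis and in sections 6.2.1 and 11.1.1. Either way, state which relationship categories qualify an event for the composite.

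The main change is one deletion, with no effect on data collection, sample size or analysis method. As a protocol amendment it needs ethics committee approval under section 14.3, so it can be carried with other changes.
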